7.3. Reporting of Concomitant Medications

Only selected concomitant medications will be recorded at each subject visit. Only the following will be reported:

- immunosuppressive drugs (including peri-transplant induction therapy),
- immunomodulators,
- antiviral drugs.

A list of the selected medications is found in the Manual of Procedures. The generic name of each medication, the dosage, the route, and the start/stop dates of administration will be recorded in the appropriate sections of the eCRF. Failure to document use of selected concomitant medications will be considered a protocol deviation.

7.4. Dosing of Immunosuppressive Drugs

Immunosuppressive (IS) drug selection and doses will be determined by the site physicians/investigator in accordance with best clinical practice and local treatment standards. Modification of immunosuppressive drug dosing in response to documented BK viremia (or other indications) may be performed at the discretion of the treating physicians/investigator. All doses and dose changes should be documented in the concomitant immunosuppressive medications section of the eCRF. Failure to document concomitant medication information will be reported as a protocol deviation during screening/surveillance and intensive monitoring periods.

Measurements of immunosuppressive drug levels are not a protocol requirement. However, IS levels that are obtained for standard-of-care medical management during the study will be recorded on the eCRF.

7.5. Measurement of Viral DNA

BKV DNA levels will be measured at the UAB Central Lab. Plasma specimens will be shipped to the UAB Central Laboratory once weekly (Monday through Thursday – see Manual of Procedures

for details) for **real-time** viral load determinations. The BKV DNA in plasma will be assayed using a quantitative PCR assay. Assays will be performed approximately once weekly and results will be shared with the site investigators as soon as they are available.

NOTE: BK PCR assays performed on specimens collected during the post-viremia follow-up period will not be run in real time; real-time results will not be available to the investigator. These can be batch-shipped at the conclusion of the follow-up period.

Retrospective analysis of urine for BKV DNA and tubular injury biomarkers will be performed in viremic subjects where correlations between viremia and viruria can be made. PCR of urine for BKV DNA **will not be** performed in real time. Urine specimens for PCR and for biomarker assays will be collected, frozen, and batch-shipped to the UAB Central Laboratory (see Manual of Procedures for details).

Plasma and urine assays for other non-BK viral pathogens will be performed retrospectively. These assays **will not be** performed in real time and results **will not be** provided to the site principal investigators in real time.

Any blood BKV DNA result obtained at the local (or reference) laboratory for standard-of-care purposes will be reported on the eCRF.

7.6. Specimen Preparation, Handling and Shipping

Guidance for specimen processing, shipping and storage will be found in the MOP.

8. STATISTICAL CONSIDERATIONS

8.1. Study Hypothesis

Elucidation of the natural history of BK viremia in renal transplant patients will identify those groups at high risk for developing BKVN who may potentially benefit from therapeutic interventions (when these become available). In particular, it is of interest to compare the change in the glomerular filtration rate (GFR) a year after transplant between the BKV viremic and non-viremic subjects. We hypothesize that BKV viremia will have a negative effect on renal function as measured by GFR.

8.2. Sample Size Considerations

8.2.1. Sample Size

[figure not shown]
We propose to enroll approximately 450 (up to a maximum of 518) patients in this study. The sample size justification is based on observing a target number of BKV viremia patients from the patients enrolled in the screening group. Table 1 below shows varying values of proportion of patients with BKV viremia. Figure 1 summarizes the probability of observing K number of BKV patients (K=30, 35, 40, 45, and 50) assuming varying values of true proportion of BKV viremia patients (3% to 17%) out of 450 enrolled patients. To interpret this graph, assume that the true proportion of BKV viremia patients is 10%. Then the probabilities of observing at least 30, 35, 40, 45, and 50 BKV viremia patients out of the 450 enrolled are about 0.99, 0.94, 0.76, 0.46, and 0.19, respectively.

In this study, we would like to target approximately 40 BKV viremia patients (up to a maximum of 60). From Figure 1, enrolling 450 subjects give us at least 90% probability of identifying at least 40 BKV viremia patients, if the true percent of BKV viremia patients is at least 11%.

Table 1

Location	Study Type	Sample size (N)	% with BKV viremia	Reference
USA ³	Prospective	200	11.5%	Brennan 2005
Spain ⁵	Prospective	156	12.2%	Munoz 2005
USA ²³	Prospective	66	16.6%	Petrov 2009
Czech Republic ²⁴	Prospective	120	6%	Girmanova 2011
USA ²⁵	Retrospective	134	16%	Koleilat 2011

Figure 1: Probability of Observing a Given Number of BKV Subjects or More as a function of True Percent with BKV viremia

We are also interested in comparing the change in GFR between those with and without BKV viremia. In this power analysis, we will only be concerned about the change from baseline (time of enrollment) to Month 12 (time post-transplant). Assuming the standard deviation of the change in GFR is assumed to be the same for those with and without BKV viremia and equals 10.9 ml/min/1.73 m² (Ref: Srinivas TR, Flechner SM, Poggio ED, et al. Glomerular filtration rate slopes have significantly improved among renal transplants in the United States. Transplantation 2010; 90:1499-505.). With 40 BKV viremia subjects and 410 non-BKV viremia subjects, we will detect a mean difference in the change in GFR of at least 5.9 ml/min/1.73 m² with 90% power between these two groups of subjects at 5% level of significance based on a t-test. In the final analysis, we will be using all available GFR data for each subject which should increase the power as more information is used. This will enable us to still use data from subjects who dropped out before the end of the study.

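### Four of the five probabilities quoted for at least K viremic subjects (450 enrolled, 10% true rate) do not match that event; the chance of at least 40 is 0.80, not 0.76

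*Combined protocol and SAP*

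**What the plan says.** Section 8.2.1 bases the sample size on finding a target number of viremic subjects among those screened: approximately 40, up to 60. Figure 1 is described as plotting the probability of reaching each of five thresholds ("K=30, 35, 40, 45, and 50") among 450 enrolled, over a range of true rates. Its caption reads "Probability of Observing a Given Number of BKV Subjects or More as a function of True Percent with BKV viremia".

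To show how the graph is read, the text tells the reader to "assume that the true proportion of BKV viremia patients is 10"%. It then says that the chances of seeing "at least 30, 35, 40, 45, and 50 BKV viremia patients out of the 450 enrolled are about 0.99, 0.94, 0.76, 0.46, and 0.19".

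The next paragraph draws the design conclusion: 450 subjects give "at least 90% probability of identifying at least 40 BKV viremia patients, if the true percent of BKV viremia patients is at least 11"%.

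**The concern.** The text and the caption both define the event as K or more. The expected count at a 10% rate is 450 × 0.10 = 45, yet the chance of at least 45 is printed as 0.46. For a binomial with a whole-number mean, the mean is also the median, so the chance of reaching or exceeding it cannot be below one half. That value alone shows that the printed numbers do not describe the stated event.

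These figures teach the reader how to use the graph that supports the sample size, and one of them is the chance of meeting the study's own target of 40. The 10% rate is also not remote: Sections 2.1.1 and 2.2.1 give 10 to 15% as the expected share of recipients with viremia. If the curves were drawn from the same calculation, they would contradict their caption.

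**Working it through.** **Inputs, all from Section 8.2.1:** n = 450 enrolled; true rate p = 0.10; K = 30, 35, 40, 45, 50; event X ≥ K. Nothing is assumed from outside.

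**Formulas.** With X ~ Binomial(450, 0.10):

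- At least K: P(X ≥ K) = 1 − P(X ≤ K − 1)
- More than K: P(X > K) = 1 − P(X ≤ K)

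The two differ by the single term P(X = K).

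**Exact results.**

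| K | Printed | P(X ≥ K) | P(X > K) | P(X = K), by subtraction | Printed − P(X ≥ K) |
|---|---|---|---|---|---|
| 30 | 0.99 | 0.99477 | 0.99142 | 0.00335 | none at two decimals |
| 35 | 0.94 | 0.95462 | 0.93603 | 0.01859 | −0.015 |
| 40 | 0.76 | 0.80488 | 0.75697 | 0.04791 | −0.045 |
| 45 | 0.46 | 0.52298 | 0.46041 | 0.06257 | −0.063 |
| 50 | 0.19 | 0.23649 | 0.19219 | 0.04430 | −0.046 |

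The stated event does not reproduce the printed set. The strict tail P(X > K) reproduces all five values to two decimals.

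**Could an approximation to P(X ≥ K) explain it?** In order of K:

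- Normal, no continuity correction: 0.991, 0.942, 0.784, 0.500, 0.216
- Normal, with continuity correction: 0.993, 0.951, 0.806, 0.531, 0.240
- Poisson with mean 45: 0.993, 0.946, 0.792, 0.520, 0.247

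None gives the printed set.

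**Could a different n explain it?** P(X ≥ K) with n = 440 is 0.9921, 0.9383, 0.7595, 0.4600, 0.1896, which also rounds to the printed values. The text says 450, so the sentence would still be wrong, but the cause cannot be settled from the documents.

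**The design conclusion.** At p = 0.11 and n = 450, P(X ≥ 40) = 0.938 and P(X > 40) = 0.915. Both exceed 0.90, so the statement holds under either tail. P(X ≥ 40) reaches 0.90 at a rate of about 10.6%.

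**The case against.** The arithmetic is hard to dispute, so the case for leaving the text alone concerns weight.

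- The values are introduced with 'about', and at K = 35 the difference is one unit in the last printed digit (0.95 against 0.94). On a tolerance of two percentage points, only K = 40, 45 and 50 fail clearly. That is a fair description of the gradation. K = 35 still differs at the precision the plan uses, and it differs in the same direction and by the same one-count shift as the others.
- The numbers only illustrate the graph. The operative statement is the one at 11%, and it is correct. This stands.
- The practical effect on the study is nil. The printed values understate the chance of success, the target is itself approximate, and the permitted enrollment of 518 would raise P(X ≥ 40) at a 10% rate to 0.968. The GFR power calculation later in Section 8.2.1 takes 40 against 410 subjects as given and uses none of these probabilities. This also stands, and it limits the severity.
- Changing the wording to 'more than K' would make all five printed numbers right. That is true, but the caption and the stated target of at least 40 both use the inclusive event, so correcting the numbers is the more consistent repair.

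Figure 1 is not available in the text reviewed, so nothing can be said about whether its curves are wrong.

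**Conclusion.** The concern holds, as a minor error. For 450 subjects and a 10% rate, four of the five printed probabilities are not those of the event named. The shortfalls run from 0.015 to 0.063, and the chance of at least 40 viremic subjects is 0.80. The text also makes 45 or more look less likely than not (0.46) when it is slightly more likely than not (0.52).

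The finding rests only on the plan's own n, rate, thresholds and event, with subjects treated as independent, as the binomial requires. A one-count error in the tail is the likely explanation but is an inference; the mismatch does not depend on it. The sample size justification is not weakened.

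**What to change.** In Section 8.2.1, restate the probabilities of at least 30, 35, 40, 45 and 50 as about 0.99 (0.995 to three decimals), 0.95, 0.80, 0.52 and 0.24. Check the code or spreadsheet behind Figure 1: if the curves plot P(X ≥ K), as the caption says, leave the figure; if they plot P(X > K), regenerate it. The 11% sentence needs no change.

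The cost is a text correction and a figure check. Enrollment, design and analysis are unaffected.

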4.1. Informed Consent and Enrollment

In an effort to capture subjects early in the course of the evolving BK infection and to avoid subjects who have already developed evidence of BKV-induced nephropathy (BKVN), this protocol will emphasize the natural history of early-onset BK viremia. Obtaining informed consent early in the peri-transplant period is encouraged, although enrollment and study-related specimen collections will not begin until ≥ 4 weeks post-transplant. The consent form will secure the subject's informed consent to participate in the screening phase as well as the intensive monitoring phase (if qualifying viremia is subsequently identified).

Consented subjects can be enrolled as early as 4 weeks and as late as 100 days following renal/renal-pancreas transplant surgery. The 4-week delay prior to enrollment and initiation of specimen collection will allow post-transplantation stabilization of renal function, immunosuppressive dosing, and other clinical parameters.

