4.2. Prospective Screening Phase

Approximately 450 subjects will be screened for BK viremia (15% over-enrollment allowed, to a maximum of 518 screened subjects). During the screening phase, subjects will submit blood (plasma) for quantitative measurement of BKV DNA approximately every 4 weeks, ± 7 days, for 6 months (timed from the date of transplantation) and then approximately every 8 weeks, ± 14 days for 6 months. Also, urine specimens will be collected at each visit and stored for subsequent testing. During the screening phase, the specified intervals between sample collections should be followed as closely as possible, but may vary with subject availability. If qualifying BK viremia is not detected, surveillance will terminate approximately 12 months after the date of transplantation (or when another study termination endpoint is reached, whichever occurs sooner).

NOTE: BKV PCR results of $\geq 10,000$ from the study central laboratory, the site laboratory, or a reference laboratory are acceptable to qualify the patient for inclusion in the Intensive Monitoring Phase of the study.

NOTE: Non-study patients who are determined to have a qualifying blood BK viral load ($\geq 10,000$ copies/ml) during the course of routine clinical care (i.e., patients not consented and not identified by prospective screening/surveillance) will also be eligible for enrollment directly into the intensive monitoring surveillance phase after providing consent as long as they remain within the window of ≤ 100 days following transplantation.

Subjects will remain in the screening/surveillance phase: 1) for 12 months post-transplantation; 2) until qualifying BK viremia is documented; 3) until renal graft failure, re-transplantation, and/or initiation of chronic dialysis occurs; 4) death; 5) until subject decides to terminate participation; 6) until the investigator decides that the subject should terminate participation; or 7) until the study closes (whichever occurs first). Reason for termination of participation in the study will be documented.

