4.4. Post-Viremia Follow-Up

Following resolution of viremia, subjects will return to the previous sampling schedule (approximately every 4 weeks, \pm 14 days) for an additional 6 months (or until another study termination endpoint is reached, whichever occurs sooner). The first follow-up visit should occur approximately 4 weeks after the BK viral load was documented to be negative.

Subjects will remain in the post-viremia follow-up phase: 1). for 6 months following resolution of the BK viremia; 2). until another study termination endpoint is reached; 3). until death; 4). until they decided to terminate participation; 5). until the investigator decides that the subject should terminate participation; or 6). until the study closes (whichever occurs first). Reason for termination of study participation will be documented.

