APPENDIX A-2: Table of Study Procedures for BK Viremia Intensive Sampling Phase

Procedures	BK Viremia diagnosis	BK viremia monitoring	Post BK Viremia Follow-Up					
	Baseline	^A Every 2 weeks +/- 7 days until resolved	Month 1	Month 2	Month 3	Month 4	Month 5	Month 6
¹ Review informed consent process	X							
^{1a} Assess BK Viremia criteria	X	X						
² Record Specific Interval History Data		X	X	X	X	X	X	X
³ Record IS trough levels		X	X	X	X	X	X	X
⁴ Obtain ≥ 10 mL of blood for viral load by PCR		X	X	X	X	X	X	X
⁴ Obtain approximately 100 mL of urine for PCR and for biomarkers		X	X	X	X	X	X	X
⁵ Record selected concomitant medications		X	X	X	X	X	X	X
⁶ Serum Creatinine, estimated GFR (local lab)		X	X	X	X	X	X	X
⁷ Urinalysis - optional (local lab)		X	X	X	X	X	X	X
Study Termination								X

LEGEND:

^A When diagnosed with BK Viremia, perform procedures every 2 weeks until viremia has resolved.

¹ Review informed consent document with subject if consented during the surveillance period.

^{1a} The BK viremia criteria includes Central Unit Lab and Local plasma PCR BK viral load results, and dates of collection and dates of results

² Subject death, loss of graft function as defined by GFR <10 mL/min/1.73 m², development of urinary outlet obstruction, development of gross hematuria, development of lymphocele acute rejection, initiation of dialysis, re-transplantation, renal biopsies – Should renal biopsy be performed per standard-of care.

³ Record lab results for immunosuppressive drug trough levels, if performed for standard of care

⁴ Collect and process blood and urine samples according to instruction outlined in Manual of Procedure

⁵ Record selected concomitant medication generic name dosage, start/stop date, and route of administration.⁶ Record results of serum creatinine and estimated, if obtained for standard of care.

⁷ Record urinalysis results performed at local lab, within 7 days of visit, for dipstick and microscopic for pH, bilirubin, blood, nitrate, protein, specific gravity, glucose, ketones, RBC/HPF, WBC/HPF, urobilinogen, leukocyte esterase

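### The GFR power calculation needs a Month 12 value from all 40 viremic subjects, but those who clear before about Month 6 are scheduled to leave before then

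*Combined protocol and SAP*

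**What the plan says.** Association between BK viremia and GFR decline is one of the two primary objectives (Section 3.1.1), and Section 8.1 frames it as a comparison one year after transplant. In the power calculation of Section 8.2.1, "we will only be concerned about the change from baseline (time of enrollment) to Month 12 (time post-transplant"). It continues: "With 40 BKV viremia subjects and 410 non-BKV viremia subjects, we will detect a mean difference" of at least 5.9 ml/min/1.73 m² with 90% power, given an SD of 10.9. There is no allowance for missing Month 12 values. The section adds only that the final analysis will use all available GFR data, including data from dropouts. Section 8.4.1 specifies a mixed model for repeated measures, and Section 8.4 rules out imputation.

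The follow-up rules differ by group:

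- **No qualifying viremia.** Section 4.2: "If qualifying BK viremia is not detected, surveillance will terminate approximately 12 months after the date of transplantation". Appendix A-1 includes a Month 12 visit.
- **Qualifying viremia (at least 10,000 copies/ml).** The screening phase lasts only "2) until qualifying BK viremia is documented". Appendix A-2 then applies: "When diagnosed with BK Viremia, perform procedures every 2 weeks until viremia has resolved", resolution being a negative PCR or fewer than 1000 copies/ml. Section 4.4 sets the end: "Subjects will remain in the post-viremia follow-up phase: 1). for 6 months following resolution of the BK viremia". Appendix A-2 marks study termination at post-viremia Month 6.

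Early viremia is sought deliberately. Section 4.1 states that "this protocol will emphasize the natural history of early-onset BK viremia". Under Section 4.2, patients found viremic in routine care up to day 100 "will also be eligible for enrollment directly into the intensive monitoring surveillance phase after providing consent".

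**The concern.** The power calculation fixes its endpoint on a transplant clock, but the viremic group is followed on a clearance clock. No section returns a cleared subject to the transplant-timed visits or asks for a Month 12 GFR. The calculation therefore counts observations that the schedule does not produce for every viremic subject.

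Two things are at stake. One is precision: the viremic group has only 40 subjects, so the contrast is sensitive to each one lost. The other is selection: whether the Month 12 value exists depends on how early the virus cleared, and only in the viremic group. Viremic subjects observed at Month 12 are those with late or persistent viremia, whose GFR course may differ from that of early clearers.

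**Working it through.** **1. Reproduce the plan's figure.** Inputs from Section 8.2.1: n₁ = 40, n₂ = 410, SD 10.9, difference 5.9, 5% level, t-test. Sidedness is not stated; two-sided reproduces the plan.

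- SE = 10.9 × √(1/40 + 1/410) = 1.806
- Noncentrality = 5.9 / 1.806 = 3.27, with 448 df
- Power = 0.903; difference detectable with 90% power = 5.87

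The stated 90% and 5.9 are confirmed, provided all 40 viremic subjects contribute a Month 12 change. A one-sided test would give 0.947.

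**2. Scheduled exit.** Last visit ≈ time of clearance + 6 months.

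| Clearance (months post-transplant) | Scheduled end |
|---|---|
| 3 | about Month 9 |
| 4 | about Month 10 |
| 5 | about Month 11 |
| 6 (about day 183) | about Month 12 |

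The earliest case is viremia found at 28 days and clearance 14 days later, which gives an exit at about Month 7.4. A patient enrolled directly with viremia, at the latest on day 100, reaches Month 12 only if viremia persists to about day 183, at least 183 − 100 = 83 days later. Counting six 4-week visits instead of 6 calendar months moves the cut-off only to about Month 6.5.

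**3. Power when a share p of the 40 exits early.** The documents do not give p; 5–50% is an assumption. The 410 others are kept.

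*Completer t-test:* n₁ = 40(1 − p), same formula as in step 1.

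*Mixed model under missing at random:* effective n₁ = 40 / [1 + (p/(1 − p))(1 − r²)]. Here r is the correlation between the last on-study change and the Month 12 change, assumed to be 0.7–0.9. For example, p = 0.4 and r = 0.7 give 40 / [1 + 0.667 × 0.51] = 29.9.

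| p | Completers | Power, t-test | 90%-power difference | Effective n₁ | Power, mixed model |
|---|---|---|---|---|---|
| 0.05 | 38 | 0.890 | 6.00 | 39.0–39.6 | 0.896–0.901 |
| 0.20 | 32 | 0.837 | 6.50 | 35.5–38.2 | 0.870–0.891 |
| 0.30 | 28 | 0.790 | 6.92 | 32.8–37.0 | 0.846–0.882 |
| 0.40 | 24 | 0.730 | 7.44 | 29.9–35.5 | 0.813–0.870 |
| 0.50 | 20 | 0.655 | 8.11 | 26.5–33.6 | 0.769–0.853 |

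A two-occasion simulation (5000 runs) agreed with the mixed-model column: 0.812–0.874 at p = 0.4 and 0.779–0.858 at p = 0.5.

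**4. More viremic subjects.** Total 450, completer t-test:

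- 50 vs 400: 0.903 at p = 0.2; 0.814 at p = 0.4
- 60 vs 390 (the cap on viremic subjects): 0.902 at p = 1/3; 0.813 at p = 0.5

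**The case against.** The strongest reply is that the plan does not analyze completers. Section 8.2.1 confines the Month 12 simplification to the power calculation, and Section 8.4.1 fits a mixed model to all GFR data. On that model the loss is about 1 to 6 points at 20–30% early exit. This stands, and the mixed-model column is the fairer measure of lost power.

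The early-exit share is also unknown and may be small: a subject must fall from at least 10,000 to below 1000 copies/ml before about Month 6. That stands too, which is why only a range is given.

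Forty is a target rather than a forecast. Four of the five rates in Table 1 (11.5% to 16.6%) imply about 52 or more viremic subjects among 450 (0.115 × 450 = 51.75). With 52 vs 398, the mixed-model formula gives power of about 0.92–0.94 at 30% exit and 0.89–0.93 at 40%. Table 1 gives no viral-load threshold, however, so the qualifying count could be lower. Extra subjects restore precision but do not remove the selective missingness.

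Finally, exit follows about six monthly GFR records after clearance, so missing at random is plausible. It may be, but Section 8.4.1 neither states that assumption nor names clearance time or viral load as model terms. For early clearers the Month 12 mean would still be extrapolated. Section 8.2.1 speaks only of subjects who dropped out, not of scheduled exit in one group.

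**Conclusion.** The concern holds. The arithmetic in Section 8.2.1 is correct, but its inputs do not match the visit schedule: viremic subjects who clear before about Month 6 have no scheduled Month 12 GFR, and subjects without qualifying viremia do. Death, dialysis, re-transplantation or withdrawal can remove the value in either group; the scheduled loss affects only the viremic group.

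The mismatch follows directly from the documents; its effect rests on assumptions. With 40 viremic subjects and 20–50% early exit, planned-model power is about 0.89–0.77 if data are missing at random and r is 0.7–0.9. Completer power is 0.84–0.66. More viremic subjects, up to the cap of 60, can offset much of this. Bias towards late or persistent viremia is possible, and no size is claimed.

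The primary endpoint (incidence) and the sample size for the viremic count are unaffected. Because GFR decline is a primary objective and the remedy is cheap, this should be fixed.

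**What to change.** Amend Section 4.4, Section 6.3 and Appendix A-2 so that, for every viremic subject who would otherwise exit earlier, serum creatinine and eGFR are recorded at the remaining transplant-timed points through Month 12. Standard-of-care values should be accepted. In Section 8.4.1, index GFR by time since transplant in both groups.

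If this is not adopted, restate the power in Section 8.2.1 for the number of viremic subjects expected to have a Month 12 value, and state in Section 8.4.1 that the mixed model relies on missing at random.

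The cost is a short amendment and a few laboratory values for each early clearer: 8 to 20 subjects if 20–50% of 40 exit early (0.2 × 40 = 8; 0.5 × 40 = 20). Section 6.3, item 4, already accepts clinical-care results, and the change fits within the 24-month maximum participation. The drawback is slightly longer data collection for these subjects.
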